## SYNOPSIS

Title	Follow up of LEAP Participants and Their Families: LEAP Trio
Sponsor	The National Institute of Allergy & Infectious Diseases, US
Legal Representative in UK	Clinical Technology Centre (International) Limited, Cambridge, United Kingdom
Conducted by	Immune Tolerance Network
Protocol Chair	[name]
Study Design Co-Primary Objectives	
 
This is a long-term assessment of the LEAP randomized controlled study of early peanut consumption. LEAP participants are followed during an extended period of ad-libitum peanut consumption and then assessed for peanut allergy and other allergic outcomes at approximately age 12. In addition, siblings and parents will be assigned to the intervention or control group based on the prior randomization of their LEAP participant sibling or child, respectively.
 
1. To assess whether early consumption of peanuts by high-risk infants results in a decreased risk of peanut allergy in children approximately 12 years of age.
 
2. To determine the prevalence of sensitization in younger siblings
 

	of LEAP participants who resided in the home at the time of the LEAP intervention, comparing younger siblings of LEAP participants who consumed peanut to younger siblings of LEAP participants who avoided peanut.
Co-Primary	LEAP Participants
Επαροιπτ	The primary endpoint is the rate of peanut allergy in LEAP participants at 144 months of age. The strategy for determination of peanut allergy is outlined in section 3.3.
	LEAP Siblings
	The primary endpoint is the rate of peanut sensitization in younger siblings who resided in the home of the LEAP participant on or before LEAP Visit 60, as assessed in the current LEAP Trio study. The strategy for determination of peanut sensitization is outlined in section

3.3.2.

Secondary	LEAP Participants, Siblings, and Parents: Clinical
Endpoints	1. Amount of peanut consumption as measured by peanut
	consumption questionnaires.
	2. Skin-prick test wheal sizes to peanut, other select foods, and aeroallergens.
	3. Specific-IgE measurements to peanut, other select foods, and aeroallergens
	
 
Eczema severity by clinical assessment of SCORAD in LEAP participants and siblings.
 

	
 
Prevalence of asthma, rhinitis and eczema evaluated using a combination of questionnaires, examinations, and lung function testing in LEAP participants and siblings.
 

	6. Prevalence of asthma, rhinitis and eczema evaluated using guestionnaires in parents.
	
 
Prevalence of peanut allergy in LEAP siblings and parents.
 
Peanut-related adverse events in LEAP participants and siblings.
 

Exploratory	LEAP Participants, Siblings, and Parents
Endpoints	1. Prevalence of allergies (other than peanut).
	2. Dietary assessment questionnaires in LEAP participants.
	3. Transepidermal Water Loss (TEWL) in LEAP participants and siblings.
	4. Household peanut consumption questionnaires and concentration of environmental peanut protein in dust collected from the participants' homes.
	LEAP Participants, Siblings, and Parents: Mechanistic Endpoints for mechanistic studies are described in section 7.
Inclusion	1. Participation in LEAP.
Criteria –	2. Age at least 114 months (9.5 years).
LEAP Participants	
 
Willingness to participate in at least one study data collection (i.e. questionnaire, skin prick testing or blood draw) procedure.
 

	4. Assent by child and informed consent by parent or legal guardian. For participants only returning a Questionnaire in any format, assent/informed consent will be implied. For participants only completing a telephone visit, assent/informed consent will be given verbally.
Exclusion Criteria – LEAP Participants	There are no exclusion criteria for LEAP participants.
Inclusion	1 Sibling of I DAD montining at
Criteria –	1. Stoling of LEAP participant.
LEAP Siblings	2. Willingness to participate in at least one study data collection (i.e. questionnaire, skin prick testing or blood draw).

	3. Assent by child and informed consent by parent or legal guardian if child is younger than 16; siblings aged 16 and over will provide their own consent. For participants only returning a Questionnaire in any format, assent/informed consent will be implied). For participants only completing a telephone visit, assent/informed consent will be given verbally.
Exclusion Criteria – LEAP Siblings	There are no exclusion criteria for LEAP siblings.
Inclusion Criteria – LEAP Parents	
 
Biological parent of LEAP participant.
 
Willingness to participate in at least one study data collection (i.e. questionnaire, skin pricking testing or blood draw).
 
Informed consent. For participants only returning a Questionnaire in any format, informed consent will be implied. For participants only completing a telephone visit, informed consent will be given verbally.
 

Exclusion Criteria – LEAP Parents	There are no exclusion criteria for LEAP parents.

#### **ABBREVIATIONS**

AE	adverse event
AD	atopic dermatitis
AUC	area under the curve
CBC	complete blood count
CFR	Code of Federal Regulations
CRD	component resolved diagnosis
CRF	case report form
CRO	contract research organization
DAIT	Division of Allergy, Immunology, & Transplantation
DSMB	Data and Safety Monitoring Board
FA	food allergy
FDA	US Food and Drug Administration
FFQ	Food Frequency Questionnaire
FLG	filaggrin
GCP	good clinical practice
ICH	International Conference on Harmonisation
ITN	Immune Tolerance Network
MedDRA	Medical Dictionary for Regulatory Activities
NCI-CTCAE	National Cancer Institute Common Terminology Criteria for Adverse Events 4.03 (published June 10, 2010)
NIAID	National Institute of Allergy and Infectious Diseases
NIH	National Institutes of Health
OAS	Oral Allergy Syndrome
PA	peanut allergy
PD	pharmacodynamics
РК	pharmacokinetics
SACCC	Statistical and Clinical Coordinating Center
SAE	serious advarse event
	schous auverse event
SAP	statistical analysis plan
SAP SCORAD	statistical analysis plan SCORing Atopic Dermatitis
SAP SCORAD TEWL	statistical analysis plan SCORing Atopic Dermatitis transepidermal water loss

WHO

World Health Organization

#### 1. BACKGROUND AND RATIONALE

#### 1.1 INITIAL STUDIES IN INFANTS AT HIGH RISK FOR ALLERGY

Food allergies and peanut allergy (PA) are becoming increasingly common conditions and are now an important public health concern. Dietary avoidance of peanut in early life has been recommended in many countries. However, there is evidence that the prevalence of PA is lower in countries such as Israel where children are fed peanut from an early age. The NIAID-funded LEAP (Learning Early About Peanut allergy) Study (Protocol ITN032AD, NCT00329784) recently demonstrated that the early consumption of peanut in high-risk infants successfully reduced the prevalence of peanut allergy at five years of age when compared to peanut avoidance (81% relative reduction, intention to treat analysis). The EAT (Enquiring About Tolerance) Study demonstrated that peanut and egg consumption during infancy reduced the rates of allergy to these allergens at 3 years of age, in a general population of infants, within the per-protocol population.

The LEAP-On Study (Protocol ITN049AD, NCT01366846) was a follow-on study to LEAP and investigated whether children who consumed peanut remained protected against developing peanut allergy even after cessation of peanut consumption for a period of 12 months. A total of 556 participants (88.5% (556/628)) from the LEAP trial were enrolled in the follow-on study and the rate of adherence to avoidance was high (90.4%) in the peanut-avoidance group, 69.3% in the peanut-consumption group). At 72 months, peanut allergy remained significantly higher in the LEAP peanut-avoidance group compared to the LEAP peanut-consumption group, 18.6% vs 4.8% (p<0.001) respectively. Three new cases of allergy developed in each group, but after 12 months of avoidance there was no significant increase in the prevalence of allergy among participants in the consumption group (3.6% [10 of 274 participants] at 60 months and 4.8% [13 of 270] at 72 months, P = 0.25). These clinical findings were associated with immunological changes (levels of Ara h2-specific peanut IgE, peanut specific IgE and IgG4 levels) suggesting immune tolerance. The key finding of the LEAP studies is that early introduction and consumption of peanut until 60 months of age causes a reduction in peanut allergy that persists at 72 months of age, even with a 12-month period of avoidance.

A follow up study of LEAP participants, and studies of their siblings and parents, are now warranted to determine if the effects of early tolerance persist to 12 years of age, to assess the impact of household exposure to peanut among siblings of LEAP participants, and to examine parental characteristics that may impact the development of food allergy. Children who participated in LEAP (and LEAP-On), any siblings, and both parents will be asked to participate in one of three research studies which together will be referred to as the "LEAP Trio" (Protocol ITN070AD):

- The **LEAP** Ad Lib Study will enroll original LEAP participants.
- The LEAP Siblings Study will enroll siblings of LEAP participants.
- The LEAP Parents Study will enroll the parents of LEAP participants.

Rationale for the study of these three separate groups is provided in following sections.

#### 1.2 RATIONALE FOR LONG-TERM FOLLOW-UP OF LEAP PARTICIPANTS DURING *AD LIBITUM* PEANUT CONSUMPTION

The LEAP study findings have been adopted by international societies, including Allergy, Pediatric and Dermatology Societies. In January, 2017 NIAID published Addendum Guidelines for the Prevention of Peanut Allergy in the United States. It is therefore becoming increasingly important to fully understand the long term clinical and nutritional outcomes of the LEAP Study beyond the 12 months study period of the LEAP-On Study and with participants having eaten peanut *ad-libitum*. The LEAP Participant cohort will be rigorously assessed for peanut allergy at 12 years of age to determine if the LEAP Study intervention achieved tolerance that is independent of ongoing peanut consumption at 12 years of age as opposed to transient desensitization that is dependent on ongoing peanut ingestion.

The LEAP-On Study demonstrated that for the peanut consumption group, their nonallergic status remained stable over 12 months of peanut avoidance. If the early-life dietary intervention in LEAP (i.e. peanut consumption) does induce a long-term effect on the natural history of peanut allergy, the most likely mechanism is one involving a longterm alteration in the morphology and function of the developing immune system. This will be further investigated in this study.

In LEAP-On, participants with peanut allergy at 72 months had higher levels of Ara h2-specific IgE compared to those who did not have peanut allergy. The mean level of Ara-h2-specific IgE, which had declined significantly in the peanut consumption group in the LEAP trial (p<0.001) remained low at 72 months, after 12 months of peanut avoidance. By contrast, the mean levels of Ara-h2-specific IgE in the peanut avoidance group were significantly higher at 60 months and 72 months compared to the peanut consumption group (p<0.001).

When considering IgG4 and the ratio of peanut specific IgG4:IgE, they were both significantly higher in the peanut consumption group compared to the peanut avoidance group (p<0.001) at 60 months but also 72 months (after a yearlong period of avoidance (p<0.001)). These findings therefore favour those parameters traditionally associated with tolerance. However, in the consumption group, values of peanut IgG4 had started to decrease, even at 30 months of age (when peanut consumption was ongoing). The longer-term trajectory of IgG4, and clinical relevance thereof, will become apparent after the determination of peanut allergy at 12 years of age in the LEAP Participant cohort.

Many children with peanut allergy develop concomitant sensitization and allergy to other peanut-related foods such as tree nuts and sesame. This adds an additional burden both in terms of quality of life and morbidity associated with living with allergic disease. Similarly, early life eczema and egg allergy have been shown to be a risk for asthma, and possibly allergic rhino-conjunctivitis. We will assess the natural history of these conditions in an atopic population and will assess whether the benefits of the LEAP intervention extend to other atopic disease and other food allergens.

The nutritional consequences of consuming peanut in the LEAP Study has been published. The current study will help determine if these benefits are sustained beyond the first six years of life and after participants have been eating peanut *ad-libitum*.

We therefore aim to further investigate the clinical, immunological and nutritional safety findings of the LEAP and LEAP-On Studies. The findings will provide an opportunity to improve our understanding of how early-life introduction of peanuts may promote the development of tolerance at 12 years of age and will serve as an additional safety evaluation of this nutritional intervention.

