5,6 ⁺	The prevalence of asthma, rhinitis and eczema will be compared between LEAP avoiders and LEAP consumers using a two-tailed, chi-squared test at the 0.05 level of significance.	The prevalence of asthma, rhinitis, and eczema will be compared between the siblings of the LEAP avoiders and LEAP consumers using a logistic regression model with a random family effect included to account for the clustering of siblings within family units and the analysis of multiple siblings.	The prevalence of asthma, rhinitis, and eczema will be compared between the parents of the LEAP avoiders and LEAP consumers using a logistic regression model with a random family effect included to account for the clustering of parents within family units.
7		The proportion of participants with peanut allergy will be compared between the siblings of the LEAP avoiders and LEAP consumers using a logistic regression model with a random family effect included to account for the clustering of siblings within family units and the analysis of multiple siblings.	The proportion of participants with peanut allergy will be compared between the parents of the LEAP avoiders and LEAP consumers using a logistic regression model with a random family effect included to account for the clustering of parents within family units.
8	The proportion of participants experiencing at least one	The proportion of participants experiencing at least one	
Protocol ITN	U/UAD	v /.0	10 December 2021

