8.3.7.1. LEAP Participants

The prevalence of asthma in the LEAP Participants in the ITT population will be compared between LEAP Consumers and LEAP Avoiders using a two-tailed, chi-squared test at the 0.05 level of significance.

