8.3.7.2. LEAP Siblings and Parents

The prevalence of asthma in the LEAP Siblings in the ITT population will be compared between LEAP Consumers and LEAP Avoiders using a logistic regression model with a random family effect included to account for the clustering of siblings within family units and the analysis of multiple siblings. Older Siblings and Younger Siblings will be analyzed separately.

The same statistical methodology will be repeated for the LEAP Parents in the ITT population.

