8.3.8.1. LEAP Participants

The prevalence of rhinitis in the LEAP Participants in the ITT population will be compared between LEAP Consumers and LEAP Avoiders using a two-tailed, chi-squared test at the 0.05 level of significance.

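### Asthma, rhinitis and eczema in LEAP participants are compared by an unadjusted chi-squared test with no planned effect estimate or interval, although the protocol names early-life risk factors for asthma and possibly rhino-conjunctivitis

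*Protocol*

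**What the plan says.** Protocol 1.2 says that "early life eczema and egg allergy have been shown to be a risk for asthma, and possibly allergic rhino-conjunctivitis", and that the study "will assess whether the benefits of the LEAP intervention extend to other atopic disease and other food allergens". Protocol 2.2 makes rhino-conjunctivitis and asthma parts (d) and (f) of the first secondary objective for LEAP participants. Eczema severity is objective 3.

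The endpoint table in Protocol 9.2 compares asthma, rhinitis and eczema prevalence in LEAP participants "using a two-tailed, chi-squared test at the 0.05 level of significance". SAP 8.3.7.1 repeats this for asthma, which "will be compared between LEAP Consumers and LEAP Avoiders using a two-tailed, chi-squared test at the 0.05 level of significance". SAP 8.3.8.1 and 8.3.6.1 do the same for rhinitis and eczema. None of these sections names a covariate, a stratum, an effect measure or an interval. SAP section 4 asks only for n (%) for categorical variables.

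Elsewhere the plan uses models:
- Siblings are compared on the same outcomes "using a logistic regression model with a random family effect included to account for the clustering of siblings within family units", and parents likewise (SAP 8.3.6.2, 8.3.7.2, 8.3.8.2).
- Peanut-related adverse events in LEAP participants, also a binary secondary endpoint, get logistic regression (SAP 8.3.10.1).
- TEWL and lung function in LEAP participants get covariates (SAP 8.4.4.1, 10.1.1).
- Peanut allergy in LEAP participants gets adjusted models and analyses within the LEAP skin-prick-test (SPT) strata (SAP 8.2.1.2).

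**The concern.** The stated question is whether benefit extends to other atopic disease. That is a question about size, and a chi-squared test returns only a p-value. A result above 0.05 could mean no effect, or a worthwhile effect that the sample could not resolve. Without a planned estimate and interval the report need not say which.

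The protocol itself also points to early-life factors that predict asthma and perhaps rhino-conjunctivitis. Participants may be seen at any age from 9.5 years (Protocol 4.1.1) to about 16.5 years (Protocol 3.1), and only those who return are analysed. Leaving prognostic factors out gives up some precision and leaves any imbalance among returners uncorrected. The comparison of returners with non-returners in SAP 6.2 names age, ethnicity, sex, peanut SPT and peanut IgE. It does not name early eczema or egg allergy, so an imbalance in those two might not be seen either.

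**Working it through.** **1. Sample size, checked against the plan's own figure.** Protocol 9.3 gives 311 avoiders and 319 consumers. At 80% enrolment that is 248.8 and 255.2. For peanut allergy at 15% vs 6%, two-sided 0.05, pooled two-proportion test:
- pooled rate = (248.8 × 0.15 + 255.2 × 0.06) / 504 = 0.1044
- SE under the null = √[0.1044 × 0.8956 × (1/248.8 + 1/255.2)] = 0.02725
- SE under the alternative = √[0.1275/248.8 + 0.0564/255.2] = 0.02708
- power = Φ[(0.09 − 1.96 × 0.02725) / 0.02708] = Φ(1.35) = 91.2%

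The protocol states 91%. At 70% enrolment the same method gives 87.2% (stated: about 87%). The sample size is therefore understood. The documents give no rate, effect size or power for asthma, rhinitis or eczema, so every rate and odds ratio below is an assumption.

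**2. What an interval would show.** With 249 and 255 children and a common prevalence p, the 95% half-width of the risk difference is 1.96 × √[p(1−p)(1/249 + 1/255)]. This is 5.2 points at p = 10%, 7.0 at 20% and 8.0 at 30%. For example, 22.5% in avoiders against 17.5% in consumers gives −5.0 points, 95% CI about −12 to +2. That is not significant, yet it is compatible with a large benefit.

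**3. Precision gained from one binary baseline factor.** Let q be the factor's frequency, and p1 and p0 the outcome rates with and without it. The share of outcome variance explained is R² = q(1−q)(p1−p0)² / [p(1−p)], and the interval narrows by 1 − √(1−R²). At p = 20%, q = 50%, OR 2: p1 = 25.4%, p0 = 14.6%, R² = 0.018, so the interval is 0.9% narrower. Over p = 10–30%, q = 30–70% and OR 1.5–4, the narrowing is 0.1% to 4.8%, equal to 0.3% to 10% more children.

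**4. Power with two binary factors** (each 50% frequent; 249 vs 255; 1,500 simulated trials per row; chi-squared test against the arm term of an adjusted logistic model):

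| Avoiders vs consumers | OR of each factor | Chi-squared | Adjusted | Gain (points) | Fall in SE of risk difference |
|---|---|---|---|---|---|
| 20% vs 11% | 2 | 80.6% | 81.0% | 0.4 | 1.1% |
| 20% vs 11% | 3 | 81.3% | 83.4% | 2.1 | 3.0% |
| 20% vs 11% | 4 | 80.7% | 85.5% | 4.8 | 4.4% |
| 30% vs 20% | 2 | 73.3% | 74.6% | 1.3 | 1.7% |
| 30% vs 20% | 3 | 70.7% | 74.3% | 3.6 | 4.5% |
| 30% vs 20% | 4 | 72.3% | 77.4% | 5.1 | 6.6% |

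The simulation error of each power is about √(0.8 × 0.2 / 1500) = 1.0 point. Both tests use the same simulated data, but the smallest gains should still be read as little or nothing.

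**5. A second set of assumptions** (504 children, 4,000 trials; OR 1.5–2.5 per SD of early eczema severity, 1.5–2.5 for egg allergy, 1.3–1.5 for sex). At about 25% vs 15%, power goes from 80.0% to 81.0% with weak factors, 80.2% to 83.0% with moderate and 81.1% to 86.2% with strong. At about 45% vs 33% it goes from 81.4% to 83.2% (weak) and 82.4% to 86.7% (moderate). With no true effect, the rejection rates are 4.5% and 4.8%, so both tests hold their level. The largest gain under any set of strengths tried was about 6 points.

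**6. Sex and age only** (sex OR 1.3–1.5, age OR 1.0–1.2 per SD; 4,000 trials). Power changes by −0.3 to +0.6 points at 25% vs 15%, and by +0.4 to +1.3 at 45% vs 33%.

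**The case against.** The case for leaving the plan alone is substantial.

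- **Validity.** A reader might infer that the unadjusted test is biased. The documents do not support this: arms follow the LEAP randomisation (SAP section 6), and the main participant analysis of peanut allergy is unadjusted too. Naming a risk factor in a rationale does not oblige a plan to adjust for it. This stands. Selective return could unbalance the arms, but nothing in the documents shows that it has.
- **What Protocol 1.2 says.** A reader might take early eczema and egg allergy as established drivers of all three outcomes. The text calls them a risk for asthma, says only *possibly* for rhino-conjunctivitis, and does not address later eczema. The prognostic argument is therefore firmest for asthma.
- **Siblings and parents.** It is tempting to say that they are given the better analysis. Their models exist to handle family clustering and carry no prognostic covariates. The fairer comparison is peanut-related adverse events in the participants themselves, where logistic regression is planned with no clustering to justify it.
- **Interpretability.** Counts by arm let a reader work out a crude difference and interval. At 15% vs 25% with 255 and 249 children this is −10 points, 95% CI about −17 to −3. So a null result would not be uninterpretable. The SAP also specifies no interval for any analysis, so the gap is general. Both points reduce the concern, but a reader's own calculation is not a pre-specified estimate.
- **Availability.** The documents do not confirm that LEAP-entry eczema and egg-allergy values are held for this analysis. If they are not, step 6 shows that the precision argument nearly vanishes.

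**Conclusion.** The point holds as a modest one. Eczema, asthma and rhinitis in LEAP participants are tested without adjustment and with no planned estimate or interval, and a better method is available at almost no cost. The loss is in efficiency and interpretability, not validity.

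Adjustment is worth about 0.4 to 6 points of power and roughly 0.1% to 7% of interval width. This assumes that eczema severity and egg allergy vary within this selected high-risk cohort, that they predict the outcomes about as strongly as assumed, and that entry values can be linked. Without those values the power gain is close to zero, and the benefit is mainly the estimate and its interval. The precision gain concerns the test and a standardised risk difference. A conditional odds ratio is a different quantity and need not be more precise. These are secondary endpoints with no stated power target, so the consequence is minor.

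**What to change.** In SAP 8.3.6.1, 8.3.7.1 and 8.3.8.1, replace the chi-squared test by logistic regression on arm, the LEAP randomisation SPT stratum, sex, age at V144 and, where held from LEAP entry, eczema severity and egg allergy. Use pre-randomisation values, not comorbidities recorded at V144, which the intervention could have affected. Report the standardised risk difference with 95% CI, naming the interval method, beside the unadjusted n (%) by arm. Add early eczema and egg allergy, if held, to the characteristics in SAP 6.2.

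If the sponsor prefers no covariates, one sentence in SAP section 4 asking for a risk difference and 95% CI with every comparison of two proportions recovers most of the value.

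The cost is SAP wording, some programming and an entry in SAP section 11, because the protocol also specifies the chi-squared test. Protocol 9.5 requires review of such a change. No new data are needed: the SAP already uses the LEAP stratum (8.2.1.2) and links LEAP visit data (8.3.4.1). The downside is a few missing entry values, which a missing-category term can carry, and slightly more analysis work.
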